4.4.2.2 Statistical Testing Strategy for Secondary Efficacy Endpoints

Secondary efficacy endpoints will be tested in the sequence presented in the hierarchical order listed in [Figure 1](#), all at the $\alpha=0.05$ level.

All p-values will be reported and will be interpreted as either confirmatory or non-confirmatory (i.e., descriptive only). The circumstances for confirmatory and for non-confirmatory interpretation of p-values are described below, and the sequence of the confirmatory tests is illustrated in [Figure 1](#).

The first secondary endpoint in the hierarchy is the time to onset of confirmed disability progression for at least 12 weeks with the initial event of neurological worsening occurring during the 96-week, double-blind, double-dummy treatment period, and the fifth secondary endpoint is the same, except progression is defined as sustained for at least 24 weeks during the 96-week comparative treatment period. The fourth secondary endpoint is the proportion of patients who have confirmed disability improvement for at least 12 weeks with the initial event of neurological improvement occurring during the 96-week, double-blind, double-dummy treatment. For these three endpoints, only when data from both Studies WA21092 and WA21093 are combined will there be sufficient statistical power to detect relevant treatment differences. For the other secondary efficacy endpoints and the primary efficacy endpoint (annualized protocol-defined relapse rate by 2 years), there is sufficient statistical power within each study to detect relevant treatment differences, without needing to combine data from the two studies.

As a consequence of this, for analyses of secondary efficacy endpoints at the individual study level:

- For the first secondary efficacy endpoint (the time to onset of confirmed disability progression for at least 12 weeks), the study-level p-value will be interpreted as non-confirmatory, due to inadequate statistical power at the study level to detect relevant treatment differences.

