- The second secondary efficacy endpoint (total number of T1 Gd-enhancing lesions at Weeks 24, 48, and 96) will be tested in a confirmatory manner if and only if, in the analysis of both studies combined, the first secondary efficacy endpoint reaches a significance level of 0.05 (i.e., pooled analysis $p \leq 0.05$). If, in the analysis of the combined studies, the first secondary efficacy endpoint pooled analysis $p > 0.05$, then the second and subsequent secondary efficacy endpoint p-values within the hierarchy will be interpreted as non-confirmatory.
- The third secondary efficacy endpoint (total number of new and/or enlarging T2 hyperintense lesions at Weeks 24, 48, and 96) will be tested in a confirmatory manner if and only if the second secondary efficacy endpoint (total number of

T1 Gd-enhancing lesions at Weeks 24, 48, and 96) reaches a significance level of 0.05 (i.e., $p \leq 0.05$). If the second secondary efficacy endpoint $p > 0.05$, then the third and subsequent secondary efficacy endpoint p-values within the hierarchy will be interpreted as non-confirmatory.

- For the fourth (proportion of patients who have confirmed disability improvement for at least 12 weeks) and fifth (time to onset of confirmed disability progression for at least 24 weeks) secondary efficacy endpoints, the study-level p-value will be interpreted as non-confirmatory, due to inadequate statistical power at the study level to detect relevant treatment differences.
- The sixth secondary efficacy endpoint (total number of new T1-hypo-intense lesions (chronic black holes) at Weeks 24, 48, and 96) will be tested in a confirmatory manner if and only if, in the analysis of the combined studies, the fifth secondary efficacy endpoint (time to onset of confirmed disability progression for at least 12 weeks) reaches a significance level of 0.05 (i.e., pooled analysis $p \geq 0.05$). If, in the analysis of both studies combined, the fifth secondary efficacy endpoint pooled analysis $p > 0.05$, then the sixth and subsequent secondary efficacy endpoint p-values within the hierarchy will be interpreted as non-confirmatory.

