- The seventh (and subsequent) secondary efficacy endpoint will be tested in a confirmatory manner if and only if the sixth (or immediately previous) secondary efficacy endpoint reaches a significance level of 0.05 (i.e., $p \leq 0.05$). If the sixth (or immediately previous) secondary efficacy endpoint $p > 0.05$, then the seventh (or current) and all subsequent secondary efficacy endpoint p-values within the hierarchy will be interpreted as non-confirmatory.

Furthermore, for analyses of secondary efficacy endpoints where data from both studies are combined (so there is sufficient statistical power for all primary and secondary efficacy endpoint comparisons):

[figure not shown]
- The first secondary efficacy endpoint (the time to onset of confirmed disability progression for at least 12 weeks) will be tested in a confirmatory manner if and only if the primary efficacy endpoint (annualized protocol-defined relapse rate by 2 years), reaches a significance level of 0.05 (i.e., pooled analysis $p \leq 0.05$). If the primary efficacy endpoint pooled analysis $p > 0.05$, then all secondary efficacy endpoint pooled analysis p-values within the hierarchy will be interpreted as non-confirmatory.
- The second (and subsequent) secondary efficacy endpoint will be tested in a confirmatory manner if and only if the first (or immediately previous) secondary efficacy endpoint reaches a significance level of 0.05 (i.e., pooled analysis $p \leq 0.05$). If the first (or immediately previous) secondary efficacy endpoint pooled analysis $p > 0.05$, then the second (or current) and all subsequent secondary efficacy endpoint pooled analysis p-values within the hierarchy will be interpreted as non-confirmatory.

The sequence of the confirmatory testing is illustrated in [Figure 1](#) below.

The arrows on the left illustrate the hierarchy of the statistical tests of Study WA21092. The arrows on the right illustrate the hierarchy of the statistical tests of Study WA21093. The boxes in the middle highlight the analyses performed in the pooled data set of WA21092 and WA21093.

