For example, for Study WA21092, the primary endpoint ARR should be positive in both studies ($p \leq 0.05$). After the poolability of both Studies WA21092 and WA21093 has been observed (see more details in the Pooled SAP), the first secondary endpoint is tested in the pooled dataset WA21092 and WA21093. Then, the analysis of T1 Gd-enhancing lesions is performed for Study WA21092. If this is statistically significant ($p \leq 0.05$), the T2 hyperintense lesions are analyzed for Study WA21092. If this is statistically significant ($p \leq 0.05$), the analysis of confirmed disability improvement is done in the pooled data of Studies WA21092 and WA21093. If this is statistically significant ($p \leq 0.05$), then the analysis of Confirmed Disability Progression for at least 24 weeks is performed in the pooled data. If this is statistically significant ($p \leq 0.05$), the Chronic Black Holes endpoint is analyzed in Study WA21092. Then, the sequence of tests continues in the order of MSFC, brain volume, SF-36 PCS, and NEDA for Study WA21092.

Figure 1 Hierarchical Order of Key Efficacy Endpoints

ARR=annualized relapse rate; CDI=Confirmed Disability Improvement; CDP=confirmed disability progression; Gd=gadolinium; MSFC=Multiple Sclerosis Functional Composite Scale; NEDA=no evidence of disease activity; SF-36 PCS=short form 36 Physical Component Summary.

4.4.2.3 Time to Onset of Confirmed Disability Progression for at Least 12 Weeks with the Initial Event of Neurological Worsening Occurring during the 96-Week, Double-Blind, Double-Dummy Treatment Period

Disability progression as measured by EDSS will be assessed in all patients by the independent examining investigator at screening and baseline visit, and every 12 weeks throughout the study until the end of the double-blind, double-dummy treatment period at Week 96, after which disability progression is assessed at Weeks 12 and 24 in the OLE

and then every 24 weeks thereafter. Additional EDSS assessments for individual patients may be requested between visits (i.e., during an MS relapse).

Section 2.4 provides additional information on the timing of this analysis.

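### SAP 4.4.2.2 states inconsistent entry conditions for a study's secondary hierarchy: the study-level bullets omit the both-studies relapse-rate condition that the worked example imposes

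*SAP*

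**What the plan says.** SAP 4.4.2.2 introduces its rules with "The circumstances for confirmatory and for non-confirmatory interpretation of p-values are described below" and also points to Figure 1. Entry to the secondary endpoints is then described in three places.

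- **Study-level bullets**, which open "As a consequence of this, for analyses of secondary efficacy endpoints at the individual study level". A study's Gd-lesion test "will be tested in a confirmatory manner if and only if, in the analysis of both studies combined, the first secondary efficacy endpoint reaches" significance at 0.05. No bullet in this list mentions ARR.
- **All-pooled bullets**, which open "Furthermore, for analyses of secondary efficacy endpoints where data from both studies are combined". The condition on pooled 12-week CDP reads "if and only if the primary efficacy endpoint (annualized protocol-defined relapse rate by 2 years), reaches a significance level of 0.05 (i.e., pooled analysis", the required pooled p-value being at most 0.05. Every later one "will be tested in a confirmatory manner if and only if the first (or immediately previous) secondary efficacy endpoint reaches a significance level", again 0.05 and always on pooled p-values.
- **Worked example**: "for Study WA21092, the primary endpoint ARR should be positive in both studies", with p ≤ 0.05. Poolability is then checked, pooled 12-week CDP is tested, and the study's own Gd and T2 lesion tests follow. After those, "the analysis of confirmed disability improvement is done in the pooled data of Studies WA21092 and WA21093", and pooled 24-week CDP comes next.

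Protocol 8.2.2 lets the first secondary endpoint be tested only if the primary endpoint is significant at 0.05. It does not say whether this means the study's own ARR, ARR in both studies, or pooled ARR.

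**The concern.** A testing hierarchy should give one answer for every pattern of results. Here, if one study misses ARR while pooled CDP is significant, the study-level bullets make that study's Gd-lesion result confirmatory and the worked example does not. A study that failed its own primary could then claim a confirmatory secondary because its sister study carried the pooled test.

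The two sequences are also not linked. Pooled confirmed disability improvement (CDI) follows pooled T2 lesions in the all-pooled bullets, but the study's own T2 lesions in the worked example. The section does not say whether one pooled p-value can be confirmatory in one chain and not in another.

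**Working it through.** **Do the rules give different answers?** Take study ARR statistics z = 1.0 (p = 0.317) and z = 3.0 (p = 0.003), with pooled CDP significant.

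- Study-level bullets: the first study's Gd test is confirmatory.
- Worked example: it is not, because one study missed ARR.
- All-pooled bullets: pooled z = (1.0 + 3.0)/√2 = 2.83, p = 0.005, so pooled CDP is confirmatory in that sequence.

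If both studies meet ARR, pooled z is at least 2 × 1.96/√2 = 2.77, so every ARR condition is met and the rules agree.

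**Inputs (SAP 2.3).** ARR 0.165 (SD 0.60) against 0.33 (SD 0.80); 400 per arm; 20% dropout with a 25% relative reduction among dropouts; stated ARR power 84%; stated pooled CDP power 80%; two-sided 0.05. Equal information from the two studies and independent endpoints are my assumptions.

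**Reproducing the stated ARR power.**

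- Difference = 0.8 × 0.165 + 0.2 × (0.25 × 0.33) = 0.1485
- SE = √((0.60² + 0.80²)/400) = 0.05, so z = 0.1485/0.05 = 2.97
- Power = Φ(2.97 − 1.96) = 0.844, against 84% stated

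**How often the conflict can arise.**

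- A given study misses ARR: 1 − 0.844 = 0.156
- Both studies meet ARR: 0.844² = 0.712; at least one misses: 0.288
- A given study misses ARR and pooled CDP is significant: 0.156 × 0.80 = 0.125
- At least one study misses ARR and pooled CDP is significant: 0.288 × 0.80 = 0.230

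With a within-study ARR–CDP correlation of 0.3 or 0.5, simulation puts the 12.5% at roughly 11% or 10%.

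**Error over a study's ARR and Gd tests when that study is null on both and the other study has the design effect.** Let π be the chance that pooled CDP is significant. Under the literal bullets the error is 0.05 + 0.95 × π × 0.05.

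- Null study has the full CDP effect: π = 0.80, error = 0.05 + 0.0475 × 0.80 = 0.088
- Null study is also null on CDP: 80% pooled power means a pooled z of mean 1.96 + 0.84 = 2.80, so one study alone contributes 2.80/2 = 1.40. Then π = Φ(1.40 − 1.96) + Φ(−1.40 − 1.96) = 0.288, and error = 0.064
- The same, with the Protocol 8.2.2.1 rule that data are not pooled unless both studies favour ocrelizumab: simulated π is about 0.25, error = 0.05 + 0.0475 × 0.25 = 0.062
- Worked example: a Gd claim also needs the study's own ARR rejection, so the error stays at 0.05

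With both studies null on everything, the literal bullets give 0.05 + 0.0475 × 0.05 = 0.052. With ARR and Gd null in both studies but a full CDP effect, they give 0.088.

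**The case against.** The strongest reply is that the plan does have an ARR gate. The worked example states one for a study's own chain, and Protocol 8.2.2 puts the primary endpoint ahead of the first secondary. The study-level bullets begin at the first secondary and are presented as a consequence of limited power on three endpoints, so they may simply take entry as given. They are also loosely drafted: as printed, the bullet for the sixth endpoint labels the fifth as 12-week CDP and reverses an inequality. Figure 1, which the section names alongside the text, is not reproduced here, and the Pooled SAP is a separate document. Either may settle the point.

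Most of this stands. A reader might infer from the bullets that study-level secondaries need no ARR success at all. The documents do not support that as the plan's rule. A related inference is an error of 1 − 0.95² = 9.75% when pooled CDP is added to the family and everything is null. That figure treats pooled CDP as ungated, whereas the all-pooled bullets, the worked example and the Protocol each put ARR before it.

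What remains is that an if-and-only-if statement leaves no room for an unstated condition, and an example is a weak place to keep the only explicit rule for a study's chain.

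**Conclusion.** The inconsistency is in the text, and it is minor: a wording conflict in a decision rule, with the worked example as the likely intended answer. That the rules are unreconciled is established only for the SAP text available here.

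It has consequences only if a study misses ARR. The 12.5%, 23% and 6.2–8.8% figures compare the literal bullets with the worked example, and rest on the planning effects, equal-sized studies and independent endpoints. The error range also needs one null study beside one at full effect, in two trials of identical design. With both studies null on everything, the excess is negligible (5.2%).

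A reader might instead compare the pooled-ARR condition, met in Φ(2.97 × √2 − 1.96) = 98.7% of trial pairs, with the both-studies condition, met in 71.2%, and take the gap of about 27.5 points as the size of the problem. The documents do not support that: the lead-in to the pooled-ARR condition confines it to analyses combining both studies, so it is not offered as the gate to a study-level test.

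**What to change.** In the study-level bullets of SAP 4.4.2.2, state that ARR must reach p ≤ 0.05 in both studies before pooled 12-week CDP is tested, and hence before each study's Gd-lesion test. Add that the all-pooled sequence opens no study-level test. Check the wording against Figure 1 and the Pooled SAP, which also bear on whether the status of pooled CDI and pooled 24-week CDP is specific to each study's chain. SAP 2.4 lists the primary CSR as completed, so record this as a dated reconciliation, not as a prospective rule.

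The cost is a few sentences and that check. Compared with the literal bullets, a study's Gd test opens in about 0.712 × 0.80 = 57% of trial pairs instead of 80%. Nothing is lost if the worked example is already the operative rule, and if both studies met ARR no reported status changes on this point.

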2.4 ANALYSIS TIMING

After the 96-week visit of the last randomized patient, approximately 12-weeks may be needed to allow the confirmation of the latest event of the 12-week confirmed disability progression. Therefore, the clinical cutoff date will be approximately 12-weeks after the last patient's 96-week visit when the status is clarified for each patient. Database lock and unblinding of the Sponsor will occur several weeks after the clinical cutoff to clarify all outstanding queries.

The sites and EDSS raters will remain blind until approximately 24-weeks after the 96-week visit of the last patient randomized, to allow the confirmation of the last 24-week confirmed disability progression, in case an updated analysis of this endpoint is requested at a later point.

The following reporting events are done / planned for this study:

Report	Clinical cutoff date	Status
Primary CSR	Opera 1: 10 April 2015 Opera 2: 12 May 2015	Completed
Pooled safety analyses for safety monitoring and Publication of updated interim results	Yearly data cut has been performed since February 2017 to conduct interim analyses used for publication purposes	Completed until 2021 and planned for subsequent years until the end of the study
Interim CSR (Time to milestone analysis)	03 January 2020	Completed
Final CSR	After the last patient last visit of the open label extension phase or Safety Follow-up Phase (31 Decemeber 2022)	Planned

CSR= clinical study report

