- The fifth secondary efficacy endpoint is the time to onset of confirmed disability progression for at least 24 weeks, with the initial event of neurological worsening occurring during the 96-week, double-blind, double-dummy treatment period, but the modality being tested here (EDSS) is identical to that of the first secondary endpoint. Given that the number of 24-week CDP events will be lower than the number of 12 week CDP events, there is likely a lower chance of achieving a statistically significant treatment difference, and hence, the 24 week CDP is listed lower than the 12 week CDP. It is, however, listed relatively higher in the hierarchy as the fifth endpoint, given the greater clinical meaningfulness of disability progression than the remaining endpoints.
- The sixth and eighth secondary endpoints, chronic black holes and brain volume, are indicators of brain tissue loss. The possible correlation of such brain-atrophy measures and long-term clinical outcomes has been suggested in other studies ([Barkhof et al. 2009](#)). Therefore, because they are imaging modalities and the correlation to clinical outcomes is weaker than the imaging endpoints that are listed higher in the hierarchy, these endpoints are listed lower in the hierarchy than the clinical endpoints.
- The EDSS does not adequately assess upper limb function and cognitive impairment; therefore, the MSFC scale is used to address this gap in clinical disability assessment. However, since the MSFC scale is not as widely used in other studies and not as well-accepted as a validated endpoint, it is listed seventh in the hierarchy.
- The SF-36 is one of the most widely used and validated instruments for measuring quality of life in patients with MS. It is, however, listed as ninth in the hierarchy below all the other clinical measures because quality-of-life instruments in general are not as widely used in confirmatory clinical studies compared with the other clinical measures.

- The tenth and final secondary endpoint is a composite measure encompassing the absence of disease activity based on clinical and MRI parameters (i.e., consisting of the primary endpoint and secondary endpoints 1, 2, and 3 above). It is a highly meaningful endpoint for patients but is listed as last in the hierarchy because it is a combination of previous secondary endpoints.

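### The SAP's condition for opening secondary endpoint 6 names 12-week instead of 24-week CDP and prints significance as pooled p ≥ 0.05

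*SAP*

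**What the plan says.** SAP 4.4.2.2 tests the secondary endpoints in a fixed order, "all at the $\alpha=0.05$ level". Endpoints 1, 4 and 5 (12-week CDP, 12-week disability improvement, 24-week CDP) are confirmatory only in the pool of the two studies. The other secondary endpoints are tested within each study.

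The bullet that opens endpoint 6 (chronic black holes) at study level has two sentences. The first gives the condition on the fifth endpoint as "time to onset of confirmed disability progression for at least 12 weeks) reaches a significance level of 0.05 (i.e., pooled analysis $p \geq 0.05". The second covers a pooled p above 0.05 on the fifth endpoint: "then the sixth and subsequent secondary efficacy endpoint p-values within the hierarchy will be interpreted as non-confirmatory".

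The SAP identifies the fifth endpoint in four other places:

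- 4.4.2.1: "The fifth secondary efficacy endpoint is the time to onset of confirmed disability progression for at least 24 weeks".
- 4.4.2.2, after defining endpoint 1 as 12-week CDP: "the fifth secondary endpoint is the same, except progression is defined as sustained for at least 24 weeks during the 96-week comparative treatment period".
- 4.4.2.2, the bullet just before the one at issue: "fifth (time to onset of confirmed disability progression for at least 24 weeks) secondary efficacy endpoints, the study-level p-value will be interpreted as non-confirmatory".
- 4.4.2.2, the worked example for Figure 1, after a significant disability-improvement result: "then the analysis of Confirmed Disability Progression for at least 24 weeks is performed in the pooled data". Black holes follow if that result has p ≤ 0.05.

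Protocol 8.2.2 states the general rule: apart from the three pooled endpoints, a secondary endpoint is tested only if the one listed before it was significant at 0.05.

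**The concern.** This sentence is an operative if-and-only-if rule. It decides whether the study-level p-value for black holes is confirmatory or descriptive. Through the next bullet it also decides the status of MSFC, brain volume, SF-36 PCS and NEDA, so five endpoints depend on it.

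Correcting only one of the slips does not give a sound sentence. With the sign corrected and the label kept, endpoint 6 opens on 12-week CDP, a test already passed at step 1, so endpoints 4 and 5 no longer protect it. With the label corrected and the sign kept, endpoint 6 opens when 24-week CDP fails. The reader of a report that cites this SAP should be able to tell which condition was used.

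**Working it through.** **Comparing the texts.** The label 12 weeks conflicts with all four places listed above. The sign conflicts with the other five conditions in the same list (endpoint 2, endpoint 3, endpoint 7 onward, and the two pooled-analysis conditions), all printed p ≤ 0.05, and with the worked example for this same step. The second sentence of the bullet contradicts the sign but does not by itself contradict the label, because it says fifth without giving a number of weeks.

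**Is either slip a reading error?** Possibly the sign: SAP 4.4.2.9 prints a stray ≤ inside the term post-baseline. The label is in words, so that explanation does not apply to it.

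**Consequence of each reading.** The SAP gives no error rate specific to this step beyond α = 0.05 two-sided, so there is no planned figure to reproduce. Assume endpoints 1 to 4 have passed and endpoints 5 and 6 are both null. The first calculation takes the two tests as independent.

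| First sentence, applied alone | False claim on 5 or 6 | False claim on 6 |
|---|---|---|
| Intended (24 weeks, p ≤ 0.05) | 0.05 | 0.05 × 0.05 = 0.0025 |
| Sign corrected, label kept | 1 − 0.95² = 0.0975 | 0.05 |
| Label corrected, sign kept | 0.05 + 0.95 × 0.05 = 0.0975 | 0.95 × 0.05 = 0.0475 |

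As printed with both slips, 12-week CDP needs p ≤ 0.05 to open endpoint 2 and p ≥ 0.05 to open endpoint 6. Both hold only at exactly 0.05, so endpoints 6 to 10 in effect never open. That loses power and does not inflate type I error.

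**Allowing for correlation.** In both one-slip readings the error is the probability of rejecting 5 or 6:

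1 − P(|Z5| < 1.96, |Z6| < 1.96), with (Z5, Z6) bivariate normal.

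Endpoint 5 is tested on pooled data and endpoint 6 in one study. For two equal studies a and b, Z5 = (Z5a + Z5b)/√2 and Z6 = Z6a. If the within-study correlation is c, then ρ = c/√2, which cannot exceed 1/√2 = 0.71.

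| c (assumed) | Error |
|---|---|
| 0 | 0.0975 |
| 0.3 | 0.0963 |
| 0.5 | 0.0942 |
| 0.7 | 0.0909 |
| 0.9 | 0.0862 |
| 1 (limit) | 0.0831 |

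A simulation of 4 million draws gave 0.0501 for the intended rule, and 0.0974, 0.0962 and 0.0863 for the one-slip readings at c = 0, 0.3 and 0.9. The documents give no correlations.

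**Applying both sentences.** If fifth in the second sentence means 24-week CDP, endpoint 6 is closed whenever 24-week CDP has p > 0.05, and no reading of the first sentence inflates the error.

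**The case against.** The strongest reply is that only one rule can have been meant. Figure 1's order governs, Protocol 8.2.2 requires the preceding endpoint to be significant, and the worked example spells the step out. On this view fifth identifies the endpoint, the parenthesis is a wrong gloss, and the sign may not be on the original page. The 0.0975 needs a reader who follows half a bullet, ignores the rest and repairs exactly one slip. It also conditions on endpoints 1 to 4 having passed: at the SAP's planned 80% power for 12-week CDP, with 2 to 4 certain and independence, it becomes 0.8 × 0.0975 = 0.078. Finally, the primary report is done, and the open-label repeats of the lesion-count endpoints are labelled exploratory, so no stated confirmatory decision still depends on the sentence.

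Much of this stands. The rule is recoverable, the sign should be checked against the original page, the error figures illustrate misreadings and are not properties of the plan taken as a whole, and nothing shows that the wrong condition was used. The mislabel still stands, in the rule itself, and the text that corrects it most fully is offered as an example. Whether the study report shows which condition was applied cannot be seen from these documents.

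**Conclusion.** The concern holds. The sentence that opens endpoint 6 at study level is wrong as written: the label certainly, the sign subject to a check of the original page. It is a drafting error in a confirmatory decision rule and does not break the testing strategy, because the surrounding text fixes the intended rule as 24-week CDP with pooled p ≤ 0.05.

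There is no inflation of type I error when the whole bullet is applied with fifth read as 24-week CDP. The conditional error of 0.083 to 0.0975, against 0.05, arises only if the first sentence is used alone with one slip repaired. It assumes that endpoints 5 and 6 are null, that 1 to 4 have passed, that the studies are of equal size, and that the within-study correlation lies between 0 and 1.

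**What to change.** In the endpoint 6 bullet of SAP 4.4.2.2, change the description of the fifth endpoint from 12 to 24 weeks and the inequality to pooled p ≤ 0.05. Leave the rest of the bullet as it is; it then agrees with the worked example.

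SAP 2.4 lists the primary report as completed, with clinical cutoffs "Opera 1: 10 April 2015 Opera 2: 12 May 2015". The correction should therefore be a dated erratum stating which condition was applied to endpoints 6 to 10 in the primary analysis. The final report is still listed as planned and can carry the note.

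The cost is a one-sentence correction and a one-line note. No reanalysis is needed if the worked example was followed. If it was not, the confirmatory or descriptive status of endpoints 6 to 10 should be restated under the corrected rule.
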